#### 5.4.2.4.3 *Correlative Protein Expression Studies*

Tissue obtained at follow-up biopsies (outlined below) will be collected, stored, and in the future analyzed by quantitative Western Blotting for phosphoprotein expression of pERBB4, pAKT, and pERK. Phospho- and total protein expressions will be compared to baseline levels, and changes will be correlated using the Fischer's exact test design for response to lapatinib. The development and translation into clinically applicable IHC testing will need to await larger studies.

**Immunoprecipitation and protein blotting.** Melanoma tissue from core needle biopsies will be gently washed three times in PBS and then lysed using 0.5–1.0 mL 1% NP-40 lysis buffer (1% Nonidet P-40, 50 mM Tris-HCl pH 7.5, 150 mM NaCl, 1× EDTA-free Complete Protease Inhibitor tablet (Roche), 1 µM sodium orthovanadate, 1 mM sodium fluoride and 0.1% β-mercaptoethanol) for 20 min on ice. Extracts are centrifuged for 10 min at 20,000g at 4 °C. Five hundred microliters of supernatant will be immunoprecipitated overnight using 20 µL of anti-ERBB4-conjugated agarose beads (Santa Cruz Biotechnology). The immunoprecipitates will be washed and subject to SDS-PAGE and protein blotting. Primary antibodies used in our analysis are anti-ERBB4 (Santa Cruz Biotechnology), anti-P-ERBB4(Y1162) (Abgent), anti-P-ERBB4(Y1284) (Cell Signaling), anti-PY20 (Zymed-Invitrogen), anti-P-ERK1/2 (T202/Y204), anti-ERK1/2, anti-P-AKT (S473), anti-AKT (Cell Signaling), and anti-α-tubulin (Calbiochem-EMD Biosciences).

**Immunoblot quantification analysis.** Scanned films from protein blot analysis of SDS-PAGE will be analyzed using ImageJ (National Institutes of Health, Bethesda, Maryland, USA). Individual bands will be quantified and plots generated to determine the intensities in each band. The data are exported to Microsoft Excel and analyzed further for the ratio of phosphoprotein to total protein.

### 5.5 General Concomitant Medication and Supportive Care Guidelines

Because there is a potential for interaction of lapatinib with other concomitantly administered drugs through the cytochrome P450 system, the case report form must capture the concurrent use of all other drugs, over-the-counter medications, or alternative therapies. The Principal Investigator should be alerted if the patient is taking any agent known to affect or with the potential to affect selected CYP450 isoenzymes.

Either the Principal Investigator or an Associate Investigator should be notified of any change in the patient's therapy, if a change is indicated. All effort should be made to give only medications that are clearly indicated for a specific medical purpose. Other anti-tumor therapy will not be permitted while the patient is on study.

Patients may be admitted as necessary to manage issues related to study medication or disease process. Anti-emetic and anti-diarrheal medications will be administered as

appropriate. Guidelines for Management of Gastrointestinal Adverse Events can be found in Appendix K of this protocol.

#### **5.6 Duration of Therapy**

In the absence of treatment delays due to adverse event(s), treatment may continue for up to 2 years (27 cycles), or until patients meet off treatment criteria as described in Section 5.8.

#### **5.7 Follow-Up Evaluations**

After completion of therapy, patients will be followed every three months during the first 2 years, every 4 months during the third year and as clinically indicated after that. After three years, patients who are continuing to respond will be contacted by telephone annually to determine disease status.

At each clinic visit the patient will undergo the following evaluation:

- History and physical examination
- Laboratory evaluations
- Chem 14 Panel {Albumin, alkaline phosphatase, total bilirubin, Total CO2 (bicarbonate), Urea nitrogen (BUN), calcium, chloride (Cl), creatinine, glucose, potassium(K), total protein, SGOT [AST], SGPT [ALT], sodium(Na)}
- CBC with differential and platelet count
- Imaging Studies

#### **5.8 Off Treatment Criteria**

- Disease progression
- Intercurrent illness that prevents further administration of treatment
- Unacceptable adverse event(s)
- Pregnancy
- Patient decides to withdraw from treatment
- Patient must start on a drug with potential CYP3A4 interaction
- General or specific changes in the patient's condition render the patient unacceptable for further treatment in the judgment of the investigator

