### **3.2 Exclusion Criteria**

3.2.1 Patients may not be currently receiving any other investigational agents.

3.2.2 Patients may not have received prior treatment with tyrosine kinase inhibitors (e.g., lapatinib, erlotinib, or gefitinib).

3.2.3 Patients currently receiving any medication known to induce/inhibit CYP3A4 as listed in Appendix D, which in the opinion of the principal investigator, would make the administration of study drug hazardous. *Note: patients receiving any strong or moderate CYP3A4 inhibitors will be excluded.*

- 3.2.4 Patients with active hepatic or biliary disease (with exception of patients with Gilbert's syndrome, asymptomatic gallstones, liver metastases or stable chronic liver disease per investigator assessment)
- 3.2.5 Patients with uncontrolled intercurrent illness including, but not limited to, ongoing or active infection, symptomatic congestive heart failure, unstable angina pectoris, cardiac arrhythmia, or psychiatric illness/social situations that would limit compliance with study requirements.
- 3.2.6 HIV-positive patients on antiretroviral therapy are excluded because most antiretrovirals are strong or moderate CYP3A4 inhibitors (please see 3.2.4 above).
- 3.2.7 Any underlying medical condition which, in the opinion of the principal investigator, will make the administration of study drug hazardous or obscure the interpretation of adverse events
- 3.2.8 Patients with any other concurrent malignancy, except for the following: adequately treated basal or squamous cell skin cancer, superficial bladder cancer, carcinoma in situ of the cervix, or any other cancer from which the patient has been disease-free for five (5) years or more.

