**Potential Drug Interactions:**

*In vitro* studies with human liver microsomes indicate that lapatinib is metabolized by CYP3A4 and CYP3A5, and to a lesser extent CYP2C19 and CYP2C8. Co-administration of lapatinib with potent or moderate CYP3A4 inhibitors (including grapefruit juice) and all CYP3A4 inducers is prohibited. Assess risk/benefit before co-administering lapatinib with weak CYP3A4 inhibitors. CYP3A4 inhibitors may decrease lapatinib metabolism (increasing levels); while CYP3A4 inducers may increase lapatinib metabolism (decreasing levels).

In human subjects, lapatanib inhibited CYP3A4 and CYP2C8 at clinically relevant concentrations. Avoid co-administration of lapatinib with drugs that are substrates of CYP3A4 or CYP2C8 and have narrow therapeutic windows.

Lapatinib potentially interacts with warfarin and quinazoline derivatives to increase INR and bleeding. Collect INR/PT determinations more frequently (e.g. weekly for the first month and weekly for a minimum of 2 weeks following lapatinib discontinuation).

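### Section 5.8 ends lapatinib for any newly needed drug with a possible CYP3A4 interaction, which is broader than the protocol's own co-administration rule in Section 8.1

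*Combined protocol and SAP*

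**What the plan says.** Section 5.8 (Off Treatment Criteria) includes the bullet "Patient must start on a drug with potential CYP3A4 interaction". It names no class (inhibitor, inducer or substrate) and no strength, and it does not call on the investigator's judgment, although the last bullet of the same list does. Section 5.6 gives the bullet its force: treatment may run for up to two years or "until patients meet off treatment criteria as described in Section 5.8".

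Four other places deal with the same drugs:

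- **Section 8.1**, on drug interactions, is graded. It states: "Co-administration of lapatinib with potent or moderate CYP3A4 inhibitors (including grapefruit juice) and all CYP3A4 inducers is prohibited". For weaker agents it says: "Assess risk/benefit before co-administering lapatinib with weak CYP3A4 inhibitors". For substrates it says: "Avoid co-administration of lapatinib with drugs that are substrates of CYP3A4 or CYP2C8 and have narrow therapeutic windows". It does not restrict other CYP3A4 substrates.
- **Section 3.2.3**, at entry, excludes a patient on an Appendix D inhibitor or inducer if the principal investigator considers the combination hazardous. It adds a fixed rule: "patients receiving any strong or moderate CYP3A4 inhibitors will be excluded". Substrates are not named.
- **Section 5.5**, during treatment, asks for notification and not for a stop: "The Principal Investigator should be alerted if the patient is taking any agent known to affect" certain CYP450 isoenzymes, or able to do so. It also foresees supportive drugs: "Anti-emetic and anti-diarrheal medications will be administered as" appropriate.
- **Appendix D** is the protocol's only list of CYP3A4 drugs. Its title is close to the phrase in 5.8. It lists substrates, inhibitors and inducers and does not grade the inhibitors by strength. Section 5.8 does not refer to it.

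**The concern.** A stopping rule that is wider than the co-administration rule can remove patients from the study drug for reasons the protocol does not itself regard as unsafe. The primary endpoint is response in at most 25 evaluable patients, with decision cutoffs at 2 of the first 16 and 5 of 25. A patient taken off lapatinib before responding, for a drug that 8.1 accepts, loses treatment without a safety gain and may lose the chance to count as a responder.

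The rule is also uneven. A patient who arrives on a weak inhibitor can be enrolled, while a patient who comes to need the same drug on treatment meets an off-treatment criterion. Since 5.8 and 8.1 give different answers, investigators can act differently on the same facts.

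**Working it through.** The plan gives no figure on this point, so the check is mainly a comparison of text.

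**Step 1. The rules side by side.**

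| CYP3A4 drug | Section 8.1 | Section 3.2.3, already taken at entry | Section 5.8, must be started on treatment |
|---|---|---|---|
| Potent or moderate inhibitor | Prohibited | Excluded | Off treatment |
| Inducer | Prohibited | Excluded if the principal investigator judges it hazardous | Off treatment |
| Weak inhibitor | Allowed after risk/benefit assessment | Excluded only if the principal investigator judges it hazardous | Off treatment |
| Narrow-window substrate | Avoid | Not named | Off treatment |
| Other substrate | Not restricted | Not named | Off treatment |

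Sections 5.8 and 8.1 agree in the first two rows. In the last three rows 5.8 goes further.

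**Step 2. Does the phrase in 5.8 reach those rows?** On its wording, yes. The part of 8.1 headed as covering potential drug interactions discusses weak inhibitors and substrates. The introduction to Appendix D describes a raised substrate concentration as a possible result of giving lapatinib. So the protocol itself treats both groups as potential interactions. No passage narrows the 5.8 bullet.

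**Step 3. Does it reach supportive care?** Only by class, and only if Appendix D is taken as the list.

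- Section 5.5 foresees anti-emetics but names none. Ondansetron is in the Appendix D substrate list and not in its inhibitor list.
- Appendix K gives fluoroquinolones as an example antibiotic, used as needed, in severe or complicated diarrhea. Ciprofloxacin and norfloxacin are in the Appendix D inhibitor list. Appendix K also holds lapatinib in that setting, and Table 5 treats the hold for Grade 3 or 4 events as temporary.
- Loperamide, octreotide, clonidine and cyproheptadine, which Appendix K names individually, are not in Appendix D.

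The documents do not say how strong an inhibitor ciprofloxacin is, or whether ondansetron counts as narrow-window. Both show how far the wording of 5.8 reaches. Whether 8.1 accepts ciprofloxacin depends on a grading the documents do not supply.

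**Step 4. Direction of any effect on the primary analysis.** The design in Section 12.1 was recomputed with exact binomials.

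- Early stopping at a 10% response rate: P(X ≤ 1), X ~ Bin(16, 0.10) = 0.9^16 + 16 × 0.1 × 0.9^15 = 0.185 + 0.329 = 0.515, against a stated 51%.
- Probability of declaring success: the sum over x = 2 to 16 of P(X = x) × P(Y ≥ 5 − x), with Y the responses among the other 9 patients. This is 0.095 at a 10% response rate (limit 0.10) and 0.903 at 30% (target 0.90).

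These figures do not depend on 5.8. Stopping lapatinib early can turn a would-be response into a non-response but cannot create a response. The count can therefore only fall, and type I error is not inflated.

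**Step 5. Size.** A size would need the rate at which patients must start such drugs, the share taken off treatment as a result, and the share of those who would have responded later. The documents give none of the three.

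**The case against.** The best case for leaving the bullet alone has four parts.

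- **The word must already limits it.** It can be read as applying only when nothing else will do, and 5.5 asks for medications only where clearly indicated. This stands in part. The word limits necessity but not class or strength, so a weak inhibitor that is medically needed still qualifies.
- **The link to Appendix D is inferred.** This stands: 5.8 does not cite it. The excess over 8.1 does not depend on the appendix, but the supportive-care examples do.
- **Section 5.5 gives a central check.** The principal investigator is to be alerted, and the principal or an associate investigator is told of changes in therapy. This reduces variation between sites, but 5.5 does not say which of the two rules then prevails.
- **A cautious stop is a legitimate choice.** It may be stricter for a new drug than for one screened at entry. That would be a fair answer if the protocol gave it, but no passage does.

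A reader might also infer more than the documents support:

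- *That the protocol forbids its own supportive care.* The overlap is by class, no individually named agent is caught, and alternatives may exist.
- *That the response rate is biased, or power lost, by some amount.* No frequency is given. Counting Appendix D entries would measure a list and not patients, and the list includes narrow-window substrates that 8.1 says to avoid and anticancer drugs barred elsewhere. Adverse event rates do not count drug starts or removals.
- *That stopped patients leave the analysis.* Off treatment is not off study (5.9). The evaluation schedule in 10.1 is not limited to patients on drug, and 12.5.2 keeps eligible patients in the main response analysis.
- *That the stop is permanent.* Section 5.8 does not say so, although it gives no route to restart.

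**Conclusion.** The point holds as a conflict between two stated rules. Section 5.8 is broader than 8.1 and stricter than 3.2.3, and read literally it could end lapatinib for drugs that 8.1 accepts. The consequence is avoidable loss of treatment. Its frequency and its effect on the response rate cannot be estimated from the documents. Any effect on the count would be downward, with no inflation of type I error.

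This rests on two assumptions: that some investigators would apply 5.8 as written instead of reading it down to 8.1, and, for the supportive-care examples only, that Appendix D is taken as the meaning of a potential interaction. It is a minor point, worth making because the conflict is plain and the correction is small.

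**What to change.** Reword the 5.8 bullet to: *Patient must start a drug whose co-administration Section 8.1 prohibits (a potent or moderate CYP3A4 inhibitor or any CYP3A4 inducer) and no acceptable alternative exists.*

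Weak inhibitors would then follow the 8.1 risk/benefit assessment, and narrow-window substrates the 8.1 advice to avoid, both with notification of the principal investigator under 5.5. Other substrates would not trigger removal.

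The cost is amendment wording for one bullet, with no change to sample size, visits or data collection. Investigators would still have to judge inhibitor strength, because Appendix D does not grade it, but 3.2.3 and 8.1 already require that. The downside is that some patients stay on lapatinib while taking a weak inhibitor or a substrate, which 8.1 already accepts.

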#### **5.9 Off Study Criteria**

Patients will be taken off study for the following:

- The patient voluntarily withdraws
- There is significant noncompliance
- General or specific changes in the patient's condition render continued participation the patient unacceptable for further follow up in the judgment of the investigator.
- Disease Progression

Note : Prior to being taken off study, all patients will be followed for 30 days or until all adverse events have resolved to grade 2 or less following the last dose of

medication. In the event of a hepatobiliary event, patients will be followed until events have resolved to grade 1 or less following the last dose of medication.

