## 7.3 Expedited Adverse Event Reporting

7.3.1 Expedited AE reporting for this study must use AdEERS (Adverse Event Expedited Reporting System), accessed via the CTEP home page (<http://ctep.cancer.gov>). The reporting procedures to be followed are presented in the “CTEP, NCI Guidelines: Adverse Event Reporting Requirements” which can be downloaded from the CTEP home page (<http://ctep.cancer.gov>). These requirements are briefly outlined in the table below (Section 7.3.3).

In the rare event when Internet connectivity is disrupted a 24-hour notification is to be made to NCI by telephone at [contact]. An electronic report **MUST** be submitted immediately upon re-establishment of internet connection. Please note that all paper AdEERS forms have been removed from the CTEP website and will no longer be accepted.

7.3.2 AdEERS is programmed for automatic electronic distribution of reports to the following individuals: Study Coordinator of the Lead Organization, Principal Investigator, and the local treating physician. AdEERS provides a copy feature for other e-mail recipients.

7.3.3 Expedited Reporting Guidelines – AdEERS Reporting Requirements for Adverse Events that occur within 30 Days of the Last Dose of the

Investigational Agent on Phase 2 and 3 Trials

Phase 2 and 3 Trials									
	Grade 1	Grade 2	Grade 2	Grade 3		Grade 3		Grades 4 & 5 	Grades 4 & 5 
	Unexpected and Expected	Unexpected	Expected	Unexpected with Hospitalization	without Hospitalization	Expected with Hospitalization	without Hospitalization	Unexpected	Expected
Unrelated Unlikely	Not Required	Not Required	Not Required	10 Calendar Days	Not Required	10 Calendar Days	Not Required	10 Calendar Days	10 Calendar Days
Possible Probable Definite	Not Required	10 Calendar Days	Not Required	10 Calendar Days	10 Calendar Days	10 Calendar Days	Not Required	24-Hour; 5 Calendar Days	10 Calendar Days

 Adverse events with attribution of possible, probable, or definite that occur greater than 30 days after the last dose of treatment with an agent under a CTEP IND require reporting as follows:  
AdEERS 24-hour notification followed by complete report within 5 calendar days for:

- Grade 4 and Grade 5 unexpected events

AdEERS 10 calendar day report:

- Grade 3 unexpected events with hospitalization or prolongation of hospitalization
- Grade 5 expected events

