##### For Patients with Measurable Disease (i.e., Target Disease)

Target Lesions	Non-Target Lesions	New Lesions	Overall Response	Best Overall Response when Confirmation is Required*
CR	CR	No	CR	≥4 wks. Confirmation**
CR	Non-CR/Non-PD	No	PR	≥4 wks. Confirmation**
CR	Not evaluated	No	PR	
PR	Non-CR/Non-PD/not evaluated	No	PR	documented at least once ≥4 wks. from baseline**
SD	Non-CR/Non-PD/not evaluated	No	SD	
PD	Any	Yes or No	PD	no prior SD, PR or CR
Any	PD***	Yes or No	PD	
Any	Any	Yes	PD	

* See RECIST 1.1 manuscript for further details on what is evidence of a new lesion.
 
** required in this non-randomized trials with response as primary endpoint
 
*** On discretion of the Principal Investigator, unequivocal progression in non-target lesions may be accepted as disease progression.
				

Note: Patients with a global deterioration of health status requiring discontinuation of treatment without objective evidence of disease progression at that time should be reported as “symptomatic deterioration.” Every effort should be made to document the objective progression even after discontinuation of treatment.
				

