**10.1.6 Progression-Free Survival**

PFS is defined as the duration of time from start of treatment to time of progression or death, whichever occurs first.

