## **12.5 Reporting and Exclusions**

12.5.1 Evaluation of toxicity – All patients will be evaluable for toxicity from the time of their first treatment with lapatinib.

12.5.2 Evaluation of response – All patients included in the treatment portion of the study must be assessed for response to treatment, even if there are major protocol treatment deviations or if they are ineligible. Each patient will be assigned one of the following categories: 1) complete response, 2) partial response, 3) stable disease, 4) progressive disease, 5) early death from malignant disease, 6) early death from toxicity, 7) early death because of other cause, or 9) unknown (not assessable, insufficient data). [Note: By arbitrary convention, category 9 usually designates the “unknown” status of any type of data in a clinical database.]

All of the patients who met the eligibility criteria (with the possible exception of those who received no study medication) should be included in the main analysis of the response rate. Patients in response categories 4-9 should be considered to have a treatment failure (disease progression). Thus, an incorrect treatment schedule or drug administration does not result in exclusion from the analysis of the response rate. Precise definitions for categories 4-9 will be protocol specific. All conclusions should be based on all eligible patients. Subanalyses may then be performed on the basis of a subset of patients, excluding those for whom major protocol deviations have been identified (e.g., early death due to other reasons, early discontinuation of treatment, major protocol violations, etc.). However, these subanalyses may not serve as the basis for drawing conclusions concerning treatment efficacy, and the reasons for excluding patients from the analysis should be clearly reported.

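### Section 5.9 lets patients leave the study without documented progression, with no stated PFS rule for them, and its safety follow-up note does not secure the 30-day adverse event window

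*Combined protocol and SAP*

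**What the plan says.** **Leaving the study.** Section 5.8 lists reasons to stop treatment, including a change in condition that rules out more treatment. Section 5.9 lists reasons to leave the study altogether. Besides progression and voluntary withdrawal, it names "There is significant noncompliance" and "General or specific changes in the patient's condition render continued participation the patient unacceptable for further follow up in the judgment of the investigator". *Significant* is not defined, and neither item asks for progression to be documented first.

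**Follow-up and PFS.** Section 5.7 plans three-monthly visits with imaging for two years after therapy. The note to the response table in 10.1.4.3, on patients who stop for global deterioration, says: "Every effort should be made to document the objective progression even after discontinuation of treatment". Section 10.1.6 reads "PFS is defined as the duration of time from start of treatment to time of progression or death", whichever is first. Section 12.4 names Kaplan-Meier. Neither says how a patient who leaves without an event is handled. The off-study column of the Section 9 calendar has no mark for radiologic evaluation or tumor measurements.

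**Safety follow-up.** The 5.9 Note says that before going off study "all patients will be followed for 30 days or until all adverse events have resolved to grade 2 or less" after the last dose. It does not say whether the earlier or the later limb governs. It adds: "In the event of a hepatobiliary event, patients will be followed until events have resolved to grade 1 or less". Section 7.3.3 is headed "AdEERS Reporting Requirements for Adverse Events that occur within 30 Days" of the last dose, and its first footnote extends reporting to certain related events after that.

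**The concern.** A patient who is failing clinically but has no RECIST progression can be taken off study on the investigator's judgment. The later progression or death, which 10.1.6 counts as a PFS event, then has no planned route into the database. If such a patient is censored at the last assessment, which is the usual Kaplan-Meier default, the censoring falls on patients close to failure. The independent-censoring assumption then breaks, and PFS looks longer than it is.

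On safety, if either limb of the Note is enough, a patient with nothing above Grade 2 at the last dose could be released before the 30-day window has been observed.

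Events that were never collected cannot be recovered at analysis. PFS and safety are both secondary objectives.

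**Working it through.** **1. The plan's own figures.** The documents give no assumed PFS, off-study rate or figure for lost adverse events. The figures Section 12.1 does give reproduce:
- Early termination at a 10% response rate: 0.9^16 + 16 × 0.1 × 0.9^15 = 0.1853 + 0.3294 = 0.5147 (stated 51%).
- Exact type I error 0.0951 and power 0.9030, against limits of 0.10 and 0.90.
- Probability of at least 25 carriers among 180 screened at 17%: 0.8892 (stated 88.9%).

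None of these depends on Section 5.9.

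**2. The route out of the study.**
- 5.8 stops treatment for changed condition. 5.7 and 10.1.4.3 then look for progression.
- 5.9 allows follow-up itself to end for changed condition or noncompliance, with progression not yet documented.
- After that exit, no section plans collection of progression or vital status.

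**3. Effect on PFS if these patients are censored.** Assume exponential PFS with true median m, and let a share s of first failures be recorded as censored. The recorded hazard is (1 − s) times the true hazard, so the estimated median is m/(1 − s):
- s = 10%: 1/0.90 = 1.11, about 11% too long.
- s = 20%: 1/0.80 = 1.25, 25% too long.

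As a check under a different mechanism, a share f of patients was censored 0.25 months before progression and the Kaplan-Meier median was computed. The true median is set at 3.0 months here. The ratio range covers true medians of 2, 3 and 4 months.

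| f (patients of 25) | Large-sample KM median, months | Ratio to truth | Median of KM medians, n = 25, months |
|---|---|---|---|
| 0% (0) | 3.00 | 1.00 | 2.99 |
| 8% (2) | 3.24 | 1.08 | 3.29 |
| 12% (3) | 3.39 | 1.12 to 1.13 | 3.41 |
| 20% (5) | 3.70 | 1.23 to 1.24 | 3.72 |
| 40% (10) | 4.89 | 1.61 to 1.63 | 4.91 |

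The two mechanisms agree closely up to 20%. If patients are followed to progression, the ratio is 1.00. If removal counts as an event, the median is slightly short instead. The direction therefore depends on a rule the plan does not state.

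**4. Effect on the safety window.** If follow-up stops on day d after the last dose, the unobserved share of the 30-day window is (30 − d)/30: 100% at day 0, 77% at day 7, 53% at day 14 and 30% at day 21. This applies only if the earlier limb governs, and only to a patient with no event above Grade 2 and no hepatobiliary event above Grade 1. On the same reading, a patient with an unresolved non-hepatobiliary Grade 3 or 4 event could leave at day 30. If the later limb governs, nothing in the window is lost.

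**The case against.** **Sections 5.8 and 5.9 set different thresholds.** One concerns fitness for treatment, the other fitness for follow-up. A deteriorating patient would normally stop treatment first, and the 10.1.4.3 note can operate in between. Section 5.3.5 allows early restaging when performance status falls or pain increases, and 6.1 requires an off-study summary with a final assessment by the treating physician. This stands, and it makes the conflict a tension rather than a flat contradiction. It does not close the gap: early restaging is optional, no exit imaging is scheduled, and nothing is planned after exit.

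**A reader might infer that PFS is overstated.** The documents do not support that without a condition. They give no censoring rule, so bias follows only if these patients are censored.

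**A reader might also infer that 5.9 contradicts 12.5.2**, under which treated patients "must be assessed for response to treatment, even if there are major protocol treatment deviations". It does not. That section governs response, provides an unknown category, and counts categories 4 to 9 as failures. The primary endpoint is not inflated; a lost confirmation scan could only lower it. A patient counted as a response failure but censored for PFS is awkward, but the two endpoints follow different rules.

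**A reader might infer that the Note does end safety follow-up before 30 days.** That is only one reading of an ambiguous *or*, and it empties the 30-day phrase of meaning for many patients. The 7.3.3 reporting duty also does not depend on being on study. Both points stand. But a duty to report does not ensure that events in a patient no longer followed come to light.

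**The size is illustrative.** The shares and medians are assumed, and the model ignores the scan schedule. At n = 25 the standard error of an exponential median is about 1/(ln 2 × √25) = 29% of the median, larger than the bias at 10% to 20%. That is correct, but bias, unlike sampling error, does not appear in the confidence interval.

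**Conclusion.** The point holds in a conditional form. Section 5.9 permits exit for noncompliance or changed condition before progression is documented, in tension with 5.7 and the 10.1.4.3 note, and the plan does not say how PFS treats such patients. If they are censored, median PFS is biased upward by about 10% to 25% for off-study shares of 10% to 20%. This assumes exponential PFS, and the shares are not taken from the documents. PFS is a secondary endpoint analyzed with exploratory intent, and the go/no-go rule uses response alone, so no trial decision changes.

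The safety point rests on an ambiguity: as worded, the Note does not guarantee ascertainment over the 30-day window in 7.3.3. Hepatobiliary events are protected by their own sentence, to Grade 1 or less.

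Both are worth correcting before data are lost. Neither threatens the primary analysis.

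**What to change.** 1. Reconcile 5.9 with 5.7 and 10.1.4.3 so that noncompliance or changed condition alone does not end collection of progression and vital status. Continue, by telephone or records if the patient cannot attend, until progression, death or withdrawal of consent. What noncompliance means for treatment is for the sponsor to settle; only the loss of follow-up is at issue here.
2. In 10.1.6 or 12.4, state how PFS treats patients who leave the study without progression and those with symptomatic deterioration. Add one sensitivity analysis that counts symptomatic deterioration as an event.
3. Reconcile the 5.9 Note with 7.3.3 so that adverse event collection covers at least the 30-day window, with the resolution conditions, including the hepatobiliary one, applying in addition.

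The cost is a few sentences, one extra analysis and occasional telephone follow-up. Reported PFS may come out slightly shorter.
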